5.0 STUDY PROCEDURES

5.1 Screening/Baseline Procedures

Assessments performed exclusively to determine eligibility for this study will be done only after obtaining informed consent. Assessments performed for clinical indications (not exclusively to determine study eligibility) may be used for baseline values even if the studies were done before informed consent was obtained.

All screening procedures must be performed within 30 days prior to registration unless otherwise stated. The screening procedures include:

5.1.1 Informed Consent

5.1.1.1. Patients with cognitive impairment will be approached for trial if all other eligibility criteria are met and determined if s/he can sign willingly or require a LAR at enrollment.

5.1.2 Medical history

Complete medical and surgical history, history of infections

5.1.3 Demographics

Age, gender, race, ethnicity

5.1.4 Review subject eligibility criteria

5.1.5 Review previous and concomitant medications

5.1.6 Physical exam including vital signs, height and weight

Vital signs (temperature, pulse, respirations, blood pressure), height, weight, office laryngoscopy and assessment of performance status (see Appendix A)

5.1.7 PET-CT or CT scan of neck

5.1.8 Adverse event assessment

Baseline adverse events will be assessed. See section 6 for Adverse Event monitoring and reporting. All acute and late adverse events from protocol radiation therapy will be reported and scored for severity using the NCI Common Terminology Criteria for Adverse Events (CTCAE) version 4.0. A copy of the CTCAE v4.0 can be downloaded from the CTEP home page (http://ctep.info.nih.gov).

5.1.9 *Pregnancy test (for females of child bearing potential)* See section 3.1.5.1 for definition.

5.1.10 QoL Questionnaires and Symptom Questionnaires

EORTC QLQ-C30, H&N 35, VHI, and EQ-5D. These forms will be referred to collectively as QoL Questionnaires.

5.2 **Procedures During Treatment**

5.2.1 Day 1

• First fraction of radiotherapy per standard, departmental stereotactic protocol

5.2.2 Weekly during treatment

- Clinical assessment including ECOG PS
- Toxicity assessment

5.2.3 Four weeks after treatment end

- Interim history
- Physical exam, vital signs, ECOG PS (vital signs are not required when patient has a Telehealth visit)
- Flexible laryngoscopy to assess tumor response and toxicity
- Quality of life and voice quality assessment

5.3 Follow-up Procedures

Patients will be seen by a radiation oncologist at 1 month (+/- 1 week) and 3 months (+/- 1 week) from the completion of treatment. More frequent visits are encouraged if the patient requires additional help with recovery and rehabilitation

Patients will then be seen every 3 months (+/- 2 weeks) for the first year, and then at least every 6 months (+/-2 weeks) until the end of the 3rd year. Subsequent and intervening follow-up visits will be made per physician preference. These protocol mandated procedures will occur at each follow-up:

- Interim history
- Physical exam, vital signs, ECOG PS (vital signs are not required when patient has a Telehealth visit)
- Laryngoscopy to assess tumor response and toxicity
- Quality of life and voice quality assessment (months 1, 3, 6, 12, 18, 24 and 36)

5.4 Time and Events Table

	Pre-study	Weekly during RT	4 weeks after completion	Follow-up*
Assessment		Х	Х	
Informed Consent	Х			
History and Physical Exam	Х		Х	Х
Performance Status	Х	Х	Х	Х
Toxicity Evaluations		Х	Х	Х
PET/CT or CT-scan of Neck	X&			X (3 months)
Laryngoscopy	Х		Х	Х
Serum or urine β-HCG (females)	X			
HR-QoL/Utility Forms 1) EQ-5D 2) EORTC-QLQ C30 + HN 35 3) VHI	X		X	X (months 1, 3, 6, 12, 18, 24 and 36)

[&] PET/CT can also be performed in place of baseline CT Neck and Chest

* These protocol mandated procedures will occur at each follow-up:

- Interim history
- Physical exam, vital signs, ECOG PS (vital signs are not required when patient has a Telehealth visit)
- Laryngoscopy to assess tumor response and toxicity
- Quality of life and voice quality will be assessed at visits 1, 3, 6, 12, 18, 24 and 36 months from the end of treatment.

Neck CT or PET-CT is required 3 months (+/- 1 week) after the completion of radiotherapy, but subsequent scans only for a clinical indication.

5.5 Removal of Subjects from Study

Subjects can be taken off the study treatment and/or study at any time at their own request, or they may be withdrawn at the discretion of the investigator for safety,

behavioral or administrative reasons. The reason(s) for discontinuation will be documented and may include:

- 5.5.1 Subject voluntarily withdraws from treatment (follow-up permitted);
- 5.5.2 Subject withdraws consent (termination of treatment and follow-up);
- 5.5.3 Subject is unable to comply with protocol requirements;
- 5.5.4 Subject demonstrates disease progression (unless continued treatment with study drug/treatment is deemed appropriate at the discretion of the investigator);
- 5.5.5 Subject experiences toxicity that makes continuation in the protocol unsafe;
- 5.5.6 Treating physician judges continuation on the study would not be in the subject's best interest;
- 5.5.7 Subject becomes pregnant (pregnancy to be reported along same timelines as a serious adverse event);
- 5.5.8 Development of second malignancy (except for basal cell carcinoma or squamous cell carcinoma of the skin) that requires treatment, which would interfere with this study;
- 5.5.9 If a research subject cannot be located to document survival after a period of 2 years, the subject may be considered "lost to follow-up." All attempts to contact the subject during the two years must be documented.

6.0 MEASUREMENT OF EFFECT

Early-stage larynx cancers are almost never visible on neck CT. The imaging is not used for response assessment but rather assessment of occult nodal disease (at diagnosis) or subsequent nodal recurrence (at 3 months). Clinical examination is sufficient at other time points.

7.0 ADVERSE EVENTS

7.1 Experimental Therapy

This treatment is hypofractionated radiotherapy as described above.

7.2 Adverse Event Monitoring

Adverse event data collection and reporting, which are required as part of every clinical trial, are done to ensure the safety of subjects enrolled in the studies as well as those who will enroll in future studies using similar agents. Adverse events are assessed in a routine manner at scheduled times during a trial. Additionally, certain adverse events must be reported in an expedited manner to allow for optimal monitoring of subject safety and care.

All subjects experiencing an adverse event, regardless of its relationship to study therapy, will be monitored until:

- the adverse event resolves or the symptoms or signs that constitute the adverse event return to baseline;
- there is a satisfactory explanation other than the study therapy for the changes observed; or
- death.

7.2.1 Definition

An adverse event is defined as any untoward or unfavorable medical occurrence in a human research study participant, including any abnormal sign (for example, abnormal physical exam or laboratory finding), symptom, clinical event, or disease, temporally associated with the subject's participation in the research, whether or not it is considered related to the subject's participation in the research.

Adverse events encompass clinical, physical and psychological harms. Adverse events occur most commonly in the context of biomedical research, although on occasion, they can occur in the context of social and behavioral research. Adverse events may be expected or unexpected.

Acute Adverse Events

Adverse events occurring in the time period from the start of treatment, through 90 days post treatment will be considered acute adverse events.

Late Adverse Events

Adverse effects occurring in the time period from the end of acute monitoring, to 36 months post treatment, will be defined as late adverse events. These events will include all adverse events reported directly to a member of the study team and will be captured, assessed, graded and reported as appropriate.

In addition, the study team will review encounters in the following select specialty categories relevant to study endpoints: radiation oncology, medical oncology, and otolaryngology. The queried encounters will be limited in scope based on categorization of events; namely, encounters that related to any head and neck or gastrointestinal event or problem.

Severity

Adverse events will be graded by a numerical score according to the defined NCI Common Terminology Criteria for Adverse Events (NCI CTCAE) and version number specified in the protocol. Adverse events not specifically defined in the NCI CTCAE will be scored on the Adverse Event log according to the general guidelines provided by the NCI CTCAE and as outlined below.

- Grade 1: Mild
- Grade 2: Moderate
- Grade 3: Severe or medically significant but not immediately life threatening
- Grade 4: Life threatening consequences
- Grade 5: Death related to the adverse event

Serious Adverse Events

OHRP and UTSW HRPP define serious adverse events as those events, occurring at any dose, which meets any of the following criteria:

- results in death;
- is life-threatening (places the subject at immediate risk of death from the event as it occurred);
- results in inpatient hospitalization^{1,2} or prolongation of existing hospitalization;
- results in a persistent or significant disability/incapacity;
- results in a congenital anomaly/birth defect; or

 based upon appropriate medical judgment, may jeopardize the subject's health and may require medical or surgical intervention to prevent one of the other outcomes listed in this definition.

Note: A "Serious adverse event" is by definition an event that meets **any** of the above criteria. Serious adverse events may or may not be related to the research project. A serious adverse event determination does not require the event to be related to the research. That is, both events completely unrelated to the condition under study and events that are expected in the context of the condition under study may be serious adverse events, independent of relatedness to the study itself. As examples, a car accident requiring \geq 24 hour inpatient admission to the hospital would be a serious adverse event for any research participant; likewise, in a study investigating end-stage cancer care, any hospitalization or death which occurs during the protocol-specified period of monitoring for adverse and serious adverse events would be a serious adverse event, even if the event observed is a primary clinical endpoint of the study.

¹Pre-planned hospitalizations or elective surgeries are not considered SAEs. Note: If events occur during a pre-planned hospitalization or surgery that prolongs the existing hospitalization, those events should be evaluated and/or reported as SAEs.

² NCI defines hospitalization for expedited AE reporting purposes as an inpatient hospital stay equal to or greater than 24 hours. Hospitalization is used as an indicator of the seriousness of the adverse event and should only be used for situations where the AE truly fits this definition and NOT for hospitalizations associated with less serious events. For example: a hospital visit where a patient is admitted for observation or minor treatment (e.g. hydration) and released in less than 24 hours. Furthermore, hospitalization for pharmacokinetic sampling is not an AE and therefore is not to be reported either as a routine AE or in an expedited report.

7.2.2 Unanticipated Problems Involving Risks to Subjects or Others (UPIRSOs):

The phrase "unanticipated problems involving risks to subjects or others" is found, but not defined in the HHS regulations at 45 CFR 46, and the FDA regulations at 21 CFR 56.108(b)(1) and 21 CFR 312.66. For device studies, part 812 uses the term unanticipated adverse device effect, which is defined in 21 CFR 812.3(s). Guidance from the regulatory agencies considers unanticipated problems to include any incident, experience, or outcome that meets ALL three (3) of the following criteria:

 Unexpected in terms of nature, severity or frequency given (a) the research procedures that are described in the protocol-related documents, such as the IRB-approved research protocol and informed consent document; and (b) the characteristics of the subject population being studied;

AND

• Related or possibly related to participation in the research (possibly related means there is a reasonable possibility that the incident, experience, or outcome may have been caused by the procedures involved in the research);

AND

 Suggests that the research places subjects or others at greater risk of harm (including physical, psychological, economic, or social harm) than was previously known or recognized. Note: According to OHRP, if the adverse event is serious, it would always suggest a greater risk of harm.

Follow-up

All adverse events will be followed up according to good medical practices.

7.3 Steps to Determine If a Serious Adverse Event Requires Expedited Reporting to the SCCC DSMC

Step 1: Identify the type of adverse event using the NCI Common Terminology Criteria for Adverse Events (CTCAE v4).

Step 2: Grade the adverse event using the NCI CTCAE v4.

Step 3: Determine whether the adverse event is related to the protocol therapy. Attribution categories are as follows:

- Definite The AE is clearly related to the study treatment.
- Probable The AE is likely related to the study treatment.
- Possible The AE may be related to the study treatment.
- Unlikely The AE may NOT be related to the study treatment.
- Unrelated The AE is clearly NOT related to the study treatment.

Note: This includes all events that occur within the acute adverse events reporting period as defined in section 7.2.1. Any event that occurs during the late adverse event period as defined in section 7.2.1 and is attributed (possibly, probably, or definitely) to the treatment must also be reported accordingly.

Step 4: Determine the prior experience of the adverse event.

Expected events are those that have been previously identified as resulting from administration of the agent. An adverse event is considered unexpected, for expedited reporting purposes only, when either the type of event or the severity of the event is not listed in:

- the current known adverse events listed in the Agent Information Section of this protocol (if applicable);
- the drug package insert (if applicable);
- the current Investigator's Brochure (if applicable)
- the Study Agent(s)/Therapy(ies) Background and Associated Known Toxicities section of this protocol

7.3.1 Reporting SAEs and UPIRSOs to the Simmons Comprehensive Cancer Center (SCCC) Data Safety Monitoring Committee (DSMC)

SAEs and UPIRSOs at all sites, which occur in research subjects on protocols for which the SCCC is the DSMC of record require reporting to the DSMC regardless of whether IRB reporting is required. All SAEs occurring during the protocol-specified monitoring period and all UPIRSOs should be submitted to the SCCC DSMC within 5 business days of the PI or delegated study team members awareness of the event(s). In addition, for participating centers other than UTSW, local IRB guidance should be followed for local reporting of serious adverse events or unanticipated problems.

The UTSW study PI is responsible for ensuring SAEs/UPIRSOs are submitted to the SCCC DSMC Coordinator. This may be facilitated by the IIT project manager, study team, subsite, or other designee. Hardcopies or electronic versions of the eIRB Reportable Event report; FDA Form #3500A forms, or other sponsor forms, if applicable; and/or any other supporting documentation available should be submitted to the DSMC Coordinator. The DSMC Coordinator forwards the information onto the DSMC Chairman who determines if immediate action is required. Follow-up eIRB reports, and all subsequent SAE or UPIRSO documentation that is available are also submitted to the DSMC Chair who determines if further action is required. (See Appendix III of the SCCC DSMC Plan for a template Serious Adverse Event Form which may be utilized).

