2.4 Endpoints

- 2.4.1 Primary endpoint: 2-year risk of local failure (i.e. anywhere in the larynx) following SBRT treatment of early glottic larynx cancer
- 2.4.2 Secondary endpoints:
 - 2.4.2.1 Patient-reported outcomes: Difference in PRO voice quality measures between baseline and 1, 3, 6, 12, 18 and 24 months following treatment:

2.4.2.1.1VHI voice-quality score2.4.2.1.2MDADI

- 2.4.2.2 Rate of grade 3-5 acute (start of treatment through 90 days from the completion of treatment) and late (after 90 days from the completion of treatment) adverse events, according to NCI's CTCAE v4.0 toxicity criteria.
- 2.4.2.3 Average patient utilities (derived from EQ-5D) at baseline, 6, 12 and 24 months from the end of treatment
- 2.4.2.5 Cumulative risk of marginal and out-of field local failure at 2 years from the start of treatment with death and prior in-field local failure as a competing risk
- 2.4.2.6 Cumulative incidence of regional failure and distant metastasis at 2 years, with death and prior locoregional failure as competing risks
- 2.4.2.7 Laryngectomy-free survival probability at 2 years
- 2.4.2.8 Overall survival at 2 years

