10.1.2.1.1 VHI voice-quality score10.1.2.1.2 EORTC QLQ30 and HN35 scores

10.1.2.2	Rate of grade 3-5 acute (start of treatment through 90 days from the completion of treatment) and late (after 90 days from the completion of treatment) adverse events, according to NCI's CTCAE v4.0 toxicity criteria.
10.1.2.3	Average patient utilities (derived from EQ-5D) at baseline and 1, 3, 6, 12, 18, 24 and 36 months from the end of treatment
10.1.2.4	Cumulative risk of marginal and out-of field local failure at 2 years from the start of treatment with death and prior in-field local failure as a competing risk
10.1.2.5	Cumulative incidence of regional failure and distant metastasis at 2 years, with death and prior locoregional failure as competing risks
10.1.2.6	Laryngectomy-free survival probability at 2 years
10.1.2.7	Overall survival at 2 years

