10.3 Data Analyses Plans

10.3.1 Primary endpoint: 2-year cumulative risk of local failure (i.e. anywhere in the larynx) following SBRT treatment of early glottic larynx cancer

This endpoint will be calculated using cumulative incidence statistics, with death as a competing risk.

10.3.2 Secondary endpoints:

Patient-reported outcomes: Difference in PRO voice quality measures between baseline and 1, 3, 6, 12, 18, 24, and 36 months following treatment:

10.3.2.1	VHI voice-quality score
10.3.2.2	EORTC QLQ-C30
	 Global health status
	 Physical functioning scale
	Role functioning scale
	Emotional functioning scale
	Cognitive functioning scale
	 Social functioning scale
10.3.2.3	EORTC HN35
	Speech
	 Social eating
	— • • • •

Social contact

These patient reported outcomes are single numeric scores that are collected at baseline, 1, 3, 6, 12, 18, 24 and 36 months from treatment. Patients with disease recurrence will be excluded. The changes in these outcomes from baseline to these timepoints will be analyzed using generalized estimated equations (GEE).

10.3.2.4 Rate of grade 3-5 acute (start of treatment through 90 days from the completion of treatment) and late (after 90 days from the completion of treatment) adverse events, according to NCI's CTCAE v4.0 toxicity criteria.

Only adverse events assessed to be definitely, probably, or possibly related to protocol treatment will be considered. The rates of all Grade 3-5 adverse events, and death during or within 30 days of discontinuation of protocol treatment will be characterized. Predictors of high-grade acute and late toxicity will be determined using multivariable logistic regression.

10.3.2.5Average patient utilities (derived from EQ-5D) at baseline, 3, 6,
12, 18, 24 and 36 months from the end of treatment

The average patient utilities (derived from EQ-5D) at baseline, 3, 6, 12, 18, 24 and 36 months from the end of treatment will be described. Changes in patient utility will be analyzed using generalized estimated equations (GEE). These models will be used to estimate the beta coefficient for dysphonia and grade 2-3 dysphagia, to produce an estimate of the utility decrement from this toxicity.

10.3.2.6 Cumulative risk of marginal and out-of-field local failure at 2 years from the start of treatment with death and prior in-field local failure as a competing risk

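### Sections 7.3 and 7.3.1 conflict on reporting late SAEs judged unrelated, and 10.3.2.4 filters by attribution a grade 3-5 endpoint that is worded without that limit

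*Combined protocol and SAP*

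**What the plan says.** **Reporting to the DSMC.** Section 7.3 sets out the steps for deciding whether an SAE needs expedited reporting. A note under its attribution step fixes the scope. For the acute period the scope is wide: "This includes all events that occur within the acute adverse events reporting period as defined in section 7.2.1". For the late period the note adds a narrower class: "Any event that occurs during the late adverse event period as defined in section 7.2.1 and is attributed (possibly, probably, or definitely) to the treatment". Section 7.2.1 dates that period: "Adverse effects occurring in the time period from the end of acute monitoring, to 36 months post treatment, will be defined as late adverse events".

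Section 7.3.1 gives the deadline with a different scope: "All SAEs occurring during the protocol-specified monitoring period and all UPIRSOs should be submitted to the SCCC DSMC within 5 business days". It contains no attribution test. Nor does the SAE definition in 7.2.1: "A serious adverse event determination does not require the event to be related to the research".

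**Toxicity endpoint.** In 2.4.2.2 the endpoint begins "Rate of grade 3-5 acute (start of treatment through 90 days from the completion of treatment) and late (after 90 days from the completion of" and then only completes the time window and names the CTCAE version. Section 10.1.2.2 has the same wording. Section 10.3.2.4 repeats it as its own title and then sets a limit: "Only adverse events assessed to be definitely, probably, or possibly related to protocol treatment will be considered". The next sentence of 10.3.2.4 promises the rates of all grade 3-5 events.

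**The concern.** Two instructions govern the same report, and two definitions govern the same endpoint. In each pair, one member depends on the investigator's judgement of causation and the other does not.

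That judgement carries more weight here than in many trials:

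- The trial has one treatment group, no reference therapy and no blinding, so no control rate shows how often similar events occur without the study treatment.
- Late effects are central to the rationale: Section 1.4 says the study aims to improve them.
- The phase I trial had three soft tissue necroses, with qualitatively higher rates in current smokers and with larger PTVs (Section 1.4). Current smokers up to one pack a day remain eligible (3.2.6, 4.1). Whether a late laryngeal event is due to radiation or to smoking is therefore a foreseeable question.
- Stopping rules are marked not applicable (7.5), and the toxicity reviews documented by the study team or the DSMC come at the end of the study (11.5). The DSMC's real-time review covers SAEs as they are reported (11.5), so it depends on a clear reporting rule.

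At stake are how promptly the DSMC sees late serious events, and what the published grade 3-5 rate means.

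**Working it through.** The documents give no design figure on this point, so there is nothing to reproduce. The check is a comparison of the texts, followed by simple arithmetic for scale.

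**Step 1: who reports what.**

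| Event | 7.3 note | 7.3.1 |
|---|---|---|
| Acute SAE, any attribution | in scope | in scope |
| Late SAE, possibly, probably or definitely related | in scope | in scope if the monitoring period includes the late period |
| Late SAE, unlikely or unrelated | outside, by implication | in scope if the monitoring period includes the late period |

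The last row is the conflict. The note separates acute from late events, and the separation serves a purpose only if some late events are left out. Section 7.3.1 leaves none out, provided its monitoring period runs to month 36. The protocol never defines that period. Section 7.2.1 supports the long reading, because it runs late events to 36 months and detaches seriousness from relatedness.

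**Step 2: endpoint against analysis.**

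- 2.4.2.2 and 10.1.2.2: grade 3-5 adverse events, acute and late, with no attribution limit. Section 7.2.1 defines an adverse event irrespective of relatedness.
- 10.3.2.4, limiting sentence: events at least possibly related. This covers acute and late events alike and works on grade, not on seriousness.
- 10.3.2.4, next sentence: all grade 3-5 events. This can mean all of the related ones, or all without limit.

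The limited rate is not the endpoint as worded, and the section does not settle which rate is to be reported. The logistic regression for predictors of high-grade toxicity in the same section inherits the ambiguity.

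**Step 3: scale.** Inputs: 25 patients (10.2); acute period to 90 days, about 3 months; late period to 36 months (7.2.1).

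- Late share of post-treatment time: (36 − 3)/36 = 33/36 = 0.92. This is calendar time, not a share of events or of risk.
- Weight of one patient: 1/25 = 0.04, or 4 percentage points, if the excluded event is that patient's only grade 3-5 event.

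Illustrations with exact (Clopper-Pearson) 95% intervals; the counts are assumed:

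| Patients with any grade 3-5 event | Rate (95% CI) | Rate if one such patient is excluded (95% CI) |
|---|---|---|
| 1 | 1/25 = 4% (0.1 to 20.4%) | 0/25 = 0% (0 to 13.7%) |
| 3 | 3/25 = 12% (2.5 to 31.2%) | 2/25 = 8% (1.0 to 26.0%) |

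The denominator may exceed 25, because every treated subject is evaluable for toxicity (4.2) and subjects who do not complete radiotherapy may be replaced (4.8). The step is 1/n, so it would then be slightly below 4 points.

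**The case against.** The strongest reply is that no report is actually lost. The 7.3 note is phrased as an addition and nowhere says that unattributed late SAEs go unreported. Section 7.3.1 carries the deadline and covers all SAEs. The DSMC also reviews adverse events quarterly (11.5), and the study team reviews late radiation oncology, medical oncology and otolaryngology encounters for head and neck or gastrointestinal problems (7.2.1). Deaths from any cause enter overall and laryngectomy-free survival whatever their attribution. If the undefined monitoring period was meant to take its scope from the 7.3 note, the two sections even agree.

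Most of this stands. A reader might infer that the plan drops late unrelated SAEs or withholds them from the DSMC. The documents do not support that: the exclusion is by implication only, it concerns expedited reporting, and other routes remain open. The reply does not remove the ambiguity, though. A period is naturally a span of time and not a causal filter, and the text of 7.2.1 points away from the reading that reconciles the two sections.

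On the endpoint, a treatment-related rate is a legitimate and common choice. It is prespecified, it includes possibly related events, and it fits objective 2.2.2, which speaks of toxicities. An unfiltered rate has its own distortion, since an accident unrelated to treatment could count. This too stands, but it argues for showing both rates. It does not make the limited rate the endpoint as worded in 2.4.2.2 and 10.1.2.2.

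**Conclusion.** Both mismatches are in the current text, and no other section resolves them. Staff handling a late SAE scored unlikely or unrelated get conflicting instructions from 7.3 and 7.3.1, mainly because the monitoring period is undefined. The analysis in 10.3.2.4 does not estimate the grade 3-5 endpoint as written, and it makes the result depend on unblinded attribution without a control group.

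The consequence is a risk of under-reporting. A reader might go further and infer that late toxicity will be understated by a particular amount, for instance that a true 12% would be published as 4%. The documents do not support that: they give no expected number of events judged unrelated, and such an example presumes that the excluded events were caused by treatment. What can be said is the step size of 4 percentage points per patient, assuming 25 evaluable patients and one qualifying event in the patient concerned. The limit in 10.3.2.4 can only lower the rate or leave it unchanged compared with the endpoint as worded. The point merits correction and does not call the design into question.

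**What to change.** - **Monitoring period.** Define it in 7.2.1 or 7.3.1 as the start of treatment to 36 months after treatment, matching the late period already in 7.2.1.
- **7.3 note.** Make it agree with 7.3.1: every SAE in that period goes to the DSMC within the existing 5 business days, with attribution recorded but not used as a filter.
- **10.3.2.4.** Report the acute and late grade 3-5 rates regardless of attribution, matching 10.1.2.2, with the treatment-related rates beside them. State which of the two definitions the logistic regression uses.

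The cost is a few sentences of amendment, a few more SAE forms in a 25-patient single-center trial, and a rate that may look less favourable. Showing the related rate alongside lets readers discount events that plainly have another cause.
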